3.8. Analysis Visit Windows

3.8.1. Definition of Study Day

Study day will be calculated from the first dosing date of study drug and derived as follows:

- For assessment dates on or after the first dosing date: Assessment Date First Dosing Date + 1
- For days prior to the first dose: Assessment Date First Dosing Date

Therefore, Study Day 1 is the day of first dose of study drug administration.

Last Dose Date is defined as the maximum, nonmissing, nonzero dose end date of treatment recorded on the Study Drug Administration eCRF form with "Study Drug Permanently Withdrawn" box checked for participants who prematurely discontinued or completed study drug according to the Study Drug Completion eCRF. Refer to Section 4.2 for missing date imputation, if necessary.

Last Study Date is the latest of the study drug start dates and end dates, the in-person or virtual visit dates, the vital sign collection dates, the questionnaire collection dates, the laboratory collection dates, and the death date (if applicable, for participants who died during the study, the death date will be the Last Study Date. For participants who died after completing the study or after prematurely discontinuing the study, the death date will not be considered for the Last Study Date).

Baseline value is defined as the last value obtained on or prior to the first dose date unless otherwise specified (see Section 3.8.3).

3.8.2. **Analysis Visit Windows**

Participant visits might not occur on protocol-specified days. Therefore, for the purpose of analysis, observations will be assigned to analysis windows.

The analysis windows for vital signs are provided in Table 3-1.

Table 3-1.	Analysis Visit V	Vindows for	Vital Signs

		Visit Window Study Day	
Analysis Visit	Nominal Study Day	Lower Limit	Upper Limit
Baseline	1	(none)	1
Day 3	3	2	4*
Day 5	5	4*	7
Day 10	10	8	12
Day 15	15	13	22
Day 29	29	23	34

If the nominal visit is a scheduled visit and the assessment is done on Day 4 (ie, Study Day = 4), assign to Day 3 or Day 5 analysis window based on the nominal visit label. If the nominal visit is an unscheduled visit or early discontinuation visit on Day 4, assign to Day 3 analysis window.

The analysis windows for SARS-CoV-2 mid-turbinate nasal swab are provided in Table 3-2.

		Visit Window Study Day	
Analysis Visit	Nominal Study Day	Lower Limit	Upper Limit
Baseline	1	(none)	1
Day 3	3	2	4*
Day 5	5	4*	7
Day 10	10	8	12
Day 15	15	13	22

Table 3-2. Analysis Visit Windows for SARS-CoV-2 Mid-turbinate Nasal Swab

* If the nominal visit is a scheduled visit and the assessment is done on Day 4 (ie, Study Day = 4), assign to Day 3 or Day 5 analysis window based on the nominal visit label. If the nominal visit is an unscheduled visit or early discontinuation visit on Day 4, assign to Day 3 analysis window.

The analysis windows for hematology, chemistry, and coagulation laboratory tests are provided in Table 3-3.

Table 3-3.	Analysis Visit Windows for Hematology, Chemistry, and Coagulation
	Laboratory Tests

		Visit Window Study Day	
Analysis Visit	Nominal Study Day	Lower Limit	Upper Limit
Baseline	1	(none)	1
Day 3	3	2	4*
Day 5	5	4*	10
Day 15	15	11	22

* If the nominal visit is a scheduled visit and the assessment is done on Day 4 (ie, Study Day = 4), assign to Day 3 or Day 5 analysis window based on the nominal visit label. If the nominal visit is an unscheduled visit or early discontinuation visit on Day 4, assign to Day 3 analysis window.

The analysis windows for urine or serum pregnancy tests are provided in Table 3-4.

Table 3-4.	Analysis V	'isit Windows :	for Urine or S	Serum Pregnancy Tests
	v			0 1

		Visit Windo	w Study Day
Analysis Visit	Nominal Study Day	Lower Limit	Upper Limit
Baseline	1	(none)	1
Day 15	15	2	22

The Symptoms of Infection with Coronavirus-19 (SIC) questionnaire will be completed daily from predose at Day 1 to Day 15 visit, then at Day 29 visit. Windows are not assigned and results will be summarized for each applicable Study Day through Day 15. For the Day 29 nominal visit, the analysis window is provided in Table 3-5.

		Visit Windo	w Study Day
Analysis Visit	Nominal Study Day	Lower Limit	Upper Limit
Baseline	1	(none)	1
Day 29	29	24	34

Table 3-5. Analysis Visit Windows for the SIC Questionnaire

3.8.3. Selection of Data in the Event of Multiple Records in an Analysis Visit Window

Depending on the statistical analysis method, single values may be required for each analysis window. For example, change from baseline by visit usually requires a single value, whereas a time-to-event analysis would not require 1 value per analysis window.

If multiple valid, nonmissing measurements exist in an analysis window, records will be chosen based on the following rules if a single value is needed:

- For baseline questionnaire data, the last nonmissing value on or prior to the first dosing date of study drug will be selected. If there are multiple records on or prior to the first dose date, the record prior to and closest to the first dose date and time will be used if available; otherwise the record after and closest to the first dose date and time will be used.
- For baseline data other than questionnaire, the last nonmissing value on or prior to the first dosing date of study drug will be selected, unless specified differently. If there are multiple records on the same day, the baseline value will be selected as follows:
 - For continuous data:
 - For SARS-CoV-2 viral load and SARS-CoV-2 infectious viral titer, if there is more than 1 record on the selected day, the latest value will be selected. If there are multiple records with the same time or no time recorded on the same day, the geometric mean value (copies/mL) will be taken.
 - For other continuous data, the average of the measurements will be taken.
 - For categorical data:
 - For SARS-CoV-2 positivity based on RT-qPCR, positivity based on infectious viral titer and Multiplex viral PCR, the worst severity (ie, a positive result, if available) will be selected.
 - For other categorical data, the lowest severity will be selected.

- For postbaseline values:
 - The record closest to the nominal day for that visit will be selected.
 - If there are 2 records that are equidistant from the nominal day, the later record will be selected.
 - If there is more than 1 record on the selected day, values will be selected for analysis as follows:
 - For SARS-CoV-2 viral load and SARS-CoV-2 infectious viral titer, if there is more than 1 record on the selected day, the latest value will be selected. If there are multiple records with the same time or no time recorded on the same day, the geometric mean value (copies/mL) will be taken.
 - For time to symptom alleviation, all records within the analysis visit window will be used.
 - For questionnaire data to be summarized, if there is more than 1 record on the selected day, the latest value will be selected.
 - For other parameters, if there is more than 1 record on the selected day, the average will be taken for continuous data and the worst severity will be taken for categorical data, unless otherwise specified.

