a Screening window is within 48 hours of the Day 1 visit. Day 1 visit may occur on the same day as screening. If the Day 1 and screening visits are the same day, do not repeat physical exam and vital signs.

- b Laboratory tests for safety will be performed on Days 1 and 5, on Days 3 and 15 when an in-person visit is conducted, and at early discontinuation.
- c Day 3 and Day 5 visits should be conducted on separate calendar days.
- d In-person is defined as a visit at a medical facility or elsewhere by a health care provider (where permitted).
- e Virtual visit is defined as an interaction with a health care professional using telephone or online-based interaction (eg, telehealth, webcast, video conferencing).

f Medical history will include the date of first COVID-19 symptoms, overall COVID-19 symptoms, all COVID-19 vaccinations prior to screening, exposure source, demographics, baseline characteristics, allergies, and all other medical history.

- g A complete physical examination must include source documentation of general appearance and the following body systems: head, neck, and thyroid; eyes, ears, nose, throat, mouth, and tongue; chest (excluding breasts); respiratory; cardiovascular; lymph nodes, abdomen; skin, hair, nails; musculoskeletal; and neurological. For participants with compensated cirrhosis, a complete physical exam must also include a clinical assessment of ascites (absent, slight, or moderate) and a clinical assessment of hepatic encephalopathy (Absent, Grade II, Grade III, or Grade IV), as described in Section 6.3.2.1. Urogenital and reproductive examination should only be completed if clinically indicated.
- h Vital signs include heart rate, respiratory rate, temperature, oxygen saturation, and blood pressure. Vital signs are collected at in-person visits only.
- i Screening: Serum ALT, bilirubin, serum creatinine, and CLcr/eGFR assessments at screening (prior to dosing) are not required unless deemed necessary by the investigator to confirm eligibility, using a local laboratory. See Appendix 11.4 for country-specific requirements.
- j All required baseline laboratory assessments should be collected prior to first study drug dose.

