- For participants with missing time of first dose, missing time is imputed using the time of SIC questionnaire assessment on the first dose date or 12:00 whichever occurs first.
- 4. Additional censoring rules due to Intercurrent event:

Hospitalization for the treatment of COVID-19 or all-cause death or Use of rescue medication (see definition in #2)

Date and Time of Day 14 SIC questionnaire assessment – Date and time of first dose.

Use Day 14 23:59 if no Day 14 SIC questionnaire assessment.

2) COVID-19 Rescue Medications

Details of COVID-19 rescue medications are provided in the table below.

Drug Class	Dictionary Level	Prohibited PREF Codes	Prohibited Ingredient, PREF, and/or ATC Decodes	
Bamlanivimab and Etesevimab	PREF	15665101001	BAMLANIVIMAB;ETESEVIMAB	
Bamlanivimab	PREF	15343501001	BAMLANIVIMAB	
Bamlanivimab	PREF	15665101001	BAMLANIVIMAB;ETESEVIMAB	
Casirivimab and Imdevimab	PREF	15585401001	CASIRIVIMAB;IMDEVIMAB	
Cilgavimab and Tixagevimab	PREF	15616901001	CILGAVIMAB;TIXAGEVIMAB	
Molnupiravir	PREF	15326101001	MOLNUPIRAVIR	
Nirmatrelvir and Ritonavir	PREF	15892101001	NIRMATRELVIR;RITONAVIR	
Remdesivir	PREF	14269001001	REMDESIVIR	
Sotrovimab	PREF	15464401001	SOTROVIMAB	
Bebtelovimab	PREF	16033001001	BEBTELOVIMAB	
Ensitrelvir	PREF	16350701001	ENSITRELVIR	
Ensitrelvir	PREF	16350702001	ENSITRELVIR FUMARIC ACID	

ATC = anatomical therapeutic chemical; PREF = preferred

Additional medication may be included during final review of concomitant medications prior to data finalization.

3) Population, denominator, and numerator for efficacy endpoints summaries of proportion

Endpoint / Summary	Population / Denominator	Numerator
Proportion of COVID-19-related hospitalization or all cause death by Day 29 Proportion of participants with all-cause hospitalization by Day 29 Proportion of participants with COVID-19-related MAVs or all-cause death by Day 29 Proportion of participants with COVID-19-related MAVs by Day 29 Proportion of participants with all-cause death by Day 29	FAPS Based on KM estimate, no explicit denominator used	Total number of events by selected visits Note: Proportions from KM estimate differ from proportion calculated directly from number of event and participants at risk

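### SAP baseline for swabs, labs and vital signs is set by first-dose date, so a post-dose Day 1 record can replace or dilute the pre-dose one

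*SAP*

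**What the plan says.** SAP 3.8.1 gives the general rule: "Baseline value is defined as the last value obtained on or prior to the first dose date unless otherwise specified". SAP 3.8.3 repeats it: "For baseline data other than questionnaire, the last nonmissing value on or prior to the first dosing date of study drug will be selected". SAP 7.2.1 and 7.3 restate it for laboratory values and vital signs. In the SAP 3.8.2 window tables for swabs, laboratory tests and vital signs, the baseline window runs through Study Day 1 and the Day 3 window opens on Study Day 2.

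When several records fall on the selected baseline day, SAP 3.8.3 splits by data type. For viral load and infectious titer, "if there is more than 1 record on the selected day, the latest value will be selected". For the rest, "For other continuous data, the average of the measurements will be taken". Neither rule is limited to samples taken before the first dose. Questionnaires are treated differently: with multiple records, "the record prior to and closest to the first dose date and time will be used if available", and a post-dose record is used only if no earlier one exists.

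In Protocol Table 1, footnote j says "All required baseline laboratory assessments should be collected prior to first study drug dose". That footnote is attached to the chemistry, coagulation and hematology row. The swab footnote (l) sets no order relative to dosing.

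**The concern.** A baseline should precede treatment. Here the first dose and the baseline samples fall on the same day, so the date alone cannot separate pre-dose from post-dose. With one viral-load record on each side of the dose, the latest-value rule always picks the post-dose one. The SAP revision table says the SARS-CoV-2 baseline rule was added to match the postbaseline rule. Taking the latest value is harmless after baseline, but at baseline it can select the wrong record.

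The value feeds the change in viral load at Day 5 (a secondary endpoint), membership of the Virology Analysis Set (baseline at or above the LLOQ) and the 6 log10 subgroup. Any early drug effect in a post-dose baseline occurs in the active arm only, so it shrinks the between-arm difference in change and lets treatment influence who is analysed. For laboratory tests, a post-dose Day 1 value absorbed into baseline cannot itself count as a treatment-emergent graded abnormality under SAP 7.2.2.1.

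**Working it through.** The plan states no figure on this point, so there is nothing to reproduce. The check applies the written rules and then bounds their effect.

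**1. Rules side by side (SAP 3.8.3)**

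| Data | Anchor | Two records on Day 1 |
|---|---|---|
| Questionnaire | first-dose date and time | closest before dose; after dose only as fallback |
| Viral load, infectious titer | first-dose date | latest |
| Other continuous | first-dose date | average |

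**2. Are the times held?** First-dose time is: SAP Appendix 3 says "For participants with missing time of first dose, missing time is imputed using the time of SIC questionnaire assessment on the first dose date", with noon as the alternative if earlier. Swab time is implied by the tie rule, which begins "If there are multiple records with the same time or no time recorded on the same day", though it may be missing for some samples. The documents do not show whether times are held for safety laboratory draws or vital signs.

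**3. Rule applied to hypothetical records, first dose assumed at 09:00** (illustrations, not trial data)

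- One swab only, at 11:00: the SAP takes it as baseline although it is post-dose.
- 08:00 = 1,000,000 and 18:00 = 500,000 copies/mL: the SAP takes log10(500,000) = 5.70; the pre-dose value is log10(1,000,000) = 6.00. The 0.30 log10 difference also moves the participant across the 6 log10 subgroup cut.
- 08:00 = 3,000 copies/mL and 18:00 detected but below 2228 (imputed as 1114): the SAP baseline is below the LLOQ, so the participant leaves the Virology Analysis Set. The pre-dose value would keep them in.

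**4. Size for the Day 5 change.** Attenuation of the mean difference = share of baselines that are post-dose × drug effect by then. Neither input is in the documents; the ranges are assumptions.

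- Low: 0.05 × 0.1 = 0.005 log10
- High: 0.10 × 0.3 = 0.03 log10

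**5. Size for set membership.** With LLOQ 2228, an early drop of d excludes only participants whose pre-dose load lies between 2228 and 2228 × 10^d.

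- d = 0.1: 2228 to 2805 copies/mL
- d = 0.3: 2228 to 4445 copies/mL

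This applies only within the assumed 5-10% with a post-dose baseline.

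**6. Averaging.** With a pre-dose value x and a post-dose value x + d, baseline becomes x + d/2. A later value at x + d then shows a change of d/2, half the true one.

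**The case against.** The strongest reply is that the case may rarely arise. Protocol Table 1 schedules one swab and one panel at Baseline/Day 1, so the latest-value and averaging rules act only if a second same-day sample exists, and nothing in the documents schedules one or reports one. Footnote j already asks for pre-dose laboratory draws. This stands, and it is why the point is minor. It does not cover a single late swab, because footnote l is silent on order.

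The early effect may also be slight. In Protocol Table 4 (healthy volunteers, 500 mg twice daily), the active metabolite in PBMCs peaked at a median of 9 h on Day 1, at 8.67 µM against 46.8 µM on Day 5. The dose and population differ from this trial, so this is indicative only, but it points the same way.

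A reader might infer three stronger things that the documents do not support.

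- *That Day 1 safety events are lost.* Protocol 7.6 requires laboratory abnormalities that need intervention or lead to study drug discontinuation to be recorded as AEs, and SAP 7.1.5.1 counts AEs with onset on or after the drug start date as treatment-emergent. Results also appear in listings. Only the graded-laboratory table and change summaries are exposed. Even there, SAP 3.8.3 takes the lowest severity for categorical baseline data; if that rule is applied to toxicity grades, the table is protected whenever a pre-dose record exists. The SAP does not say which rule governs baseline grades.
- *That the primary analysis is affected.* The primary and key secondary event endpoints use no viral-load change. FAPS positivity is also set by date, but any positive baseline result qualifies, so a later negative cannot displace an earlier positive.
- *That the rule could create a false positive for viral load.* If the early effect is a reduction in viral load, the bias runs toward no effect.

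**Conclusion.** The rule is wrong for the case it addresses: when Day 1 holds both a pre-dose and a post-dose viral-load record, it selects the post-dose one, and it averages other continuous data across the dose. The section's own questionnaire rule shows that a time-based preference was workable.

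The effect is probably small: 0.005 to 0.03 log10 toward no effect at Day 5, with set membership at risk only in a narrow band above the LLOQ. Both sizes rest on the assumed 5-10% and 0.1-0.3 log10. The documents do not say how often post-dose Day 1 samples occurred, so it would go too far to conclude that the baseline data are in fact contaminated. This is a low-cost improvement, not a threat to the trial's conclusions.

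**What to change.** Change SAP 3.8.1 and 3.8.3 only (with matching wording in 7.2.1 and 7.3):

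- Where collection time and first-dose time are both known, take as baseline the last record at or before first-dose date and time. Apply this to viral load and infectious titer, and to laboratory tests and vital signs where times are recorded.
- Do not average in records known to be post-dose.
- Keep the present date rule where either time is missing.
- If only a post-dose Day 1 swab exists, keep it as a fallback, as the questionnaire rule does. Report the number of such participants by arm, and rerun the Day 5 viral-load analysis without them as a sensitivity analysis.

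The fallback avoids dropping participants from the Virology Analysis Set. It also avoids relabelling Day 1 records as postbaseline, where they would have no visit window. Amending the swab footnote in the protocol would achieve nothing now: SAP 2.3 records that enrollment stopped on 06 October 2023.

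The cost is a little programming and one extra table. If the SAP is already final, SAP Section 1 provides for documenting the change in the CSR.

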4. SUBJECT DISPOSITION

4.1. Subject Enrollment and Disposition

Key study dates (ie, first participant screened, first participant randomized, last participant randomized, last participant last visit for the primary endpoint, and last participant last visit for the CSR) will be provided.

A summary of participant enrollment will be provided by treatment group for each investigator within a country, and overall using the All Randomized Analysis Set. The summary will present the number and percentage of participants enrolled. For each column, the denominator for the percentage calculation will be the total number of participants analyzed for that column.

A similar enrollment table will be provided by randomization stratum. The denominator for the percentage of participants in the stratum will be the total number of enrolled participants. If there are discrepancies in the value used for stratification assignment between the IXRS and the clinical database, the value collected in the clinical database will be used for the summary. A listing of participants with discrepancies in the value used for stratification assignment between the IXRS and the clinical database at the time of data finalization will be provided, if applicable.

The randomization schedule used for the study will be provided as an appendix to the CSR.

A summary of participant disposition will be provided by treatment group and overall. This summary will present the number of participants screened, the number of participants who met all eligibility criteria but were not randomized with reasons these participants were not randomized, the number of participants randomized, and the number of participants in each of the categories listed below:

- Safety Analysis Set
- FAS
- FAPS
- Completed study drug
- Did not complete study drug with reasons for premature discontinuation of study drug
- Completed study
- Did not complete the study with reasons for premature discontinuation of study

For the status of study drug and study completion and reasons for premature discontinuation, the number and percentage of participants in each category will be provided. The denominator for the percentage calculation will be the number of participants in the Safety Analysis Set. In addition, a flowchart will be provided to depict the disposition.

A by-participant listing of reasons for premature study drug or study discontinuation will be provided by participant ID number in ascending order.

4.2. Extent of Study Drug Exposure

4.2.1. Duration of Exposure to Study Drug

Total duration of exposure to study drug and number of tablets taken will be summarized by treatment group for the Safety Analysis Set.

A by-participant listing of study drug administration and drug accountability will be provided separately by participant ID number (in ascending order).

Total duration of exposure (in days) to study drug will be defined as last dosing date minus first dosing date plus 1. If the last study drug dosing date is missing for a participant, the last dose date is imputed as the earliest date from the following:

- Day 5 if the participant took 2 tablets on Day 1
- Day 6 if the participant took 1 tablet on Day 1
- Last study visit date

Study day for the imputed last dose day will not exceed Day 6.

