#### **3.3. Protocol-Specific Discontinuation Criteria**

#### **3.3.1.** Criteria for Early Discontinuation for the Individual Participants

3.3.1.1. Criteria for Early Discontinuation for the Individual Participants From Study Intervention

Study drug will be discontinued in the following instances:

- An SAE suspected to be related to study drug.
- Any  $\geq$  Grade 3 clinically significant AE suspected to be related to study drug.
- An AE, or worsening of clinical condition requiring clinical intervention, that would, in the judgment of the investigator, affect assessments of clinical status to a significant degree.
- Any ≥ Grade 3 clinically significant laboratory abnormality (if confirmed by repeat testing) suspected to be related to study drug.
   Except if baseline or on-treatment CLcr < 50 mL/min or eGFR < 50 mL/min/1.73m^2, then study drug is to be discontinued without confirmation by repeat testing and irrespective of relatedness.
- Unacceptable toxicity, as defined in Section 7.7, or toxicity that, in the judgment of the investigator, compromises the ability to continue study-specific procedures or is considered not to be in the participant's best interest.
- Baseline or on-treatment alanine aminotransferase (ALT)  $\geq$  5 × ULN.

- Baseline or on-treatment bilirubin  $\ge 2 \times ULN$  ( $\ge 3 \times ULN$  for participants with Gilbert's syndrome).
- Participant request to discontinue for any reason.
- Participant noncompliance.
- Pregnancy (refer to Appendix 11.3).
- Discontinuation of the study by sponsor.

If a participant discontinues study drug, every attempt should be made to keep the participant in the study and continue to perform the required study-related follow-up and procedures.

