4.2.2. Total Number of Tablets Administered

The total number of tablets administered will be summarized using descriptive statistics.

The presumed total number of tablets administered to a participant will be determined by the data collected on the drug accountability CRF using the following formula:

Total Number of Tablets Administered =

$$\left(\sum$$
 No. of Tablets Dispensed $\right) - \left(\sum$ No. of Tablets Returned $\right)$

The maximum tablets administered is 10 tablets.

For missing number of tablets returned, imputation rules are described in programming specifications.

No formal statistical testing is planned.

A by-participant listing of study drug administration and drug accountability will be provided separately by participant ID number (in ascending order).

4.3. **Protocol Deviations**

Participants who did not meet the eligibility criteria for study entry but were enrolled in the study, will be summarized regardless of whether they were exempted by the sponsor or not. The summary will present the number and percentage of participants who did not meet at least 1 eligibility criterion and the number of participants who did not meet specific criteria by treatment group based on the All Randomized Analysis Set. A by-participant listing will be provided for all randomized participants who did not meet at least 1 eligibility (inclusion or exclusion) criterion. The listing will present the eligibility criterion (or criteria if more than 1 deviation) that participants did not meet and related comments, if collected.

Protocol deviations occurring after participants entered the study are documented during routine monitoring. The number and percentage of participants with important protocol deviations and the total number of important protocol deviations by deviation category (eg, eligibility criteria, informed consent) will be summarized by treatment group for the All Randomized Analysis Set. A by-participant listing will be provided for those participants with important protocol deviation.

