7.4.2. Concomitant Medications

Concomitant medications are defined as medications taken while a participant took study drug. Day 1 to Day 29 medications are defined as medications taken from Day 1 to Day 29. Use of concomitant medications and Day 1 to Day 29 medications will be summarized separately by preferred name using the number and percentage of participants for each treatment group. A participant reporting the same medication more than once will be counted only once when calculating the number and percentage of participants who received that medication. The summary will be ordered by preferred term in descending overall frequency. For drugs with the same frequency, sorting will be done alphabetically. COVID-19 rescue medications (see Appendix 3) taken postbaseline will be listed and summarized if there are sufficient data.

For the purposes of analysis, any medications with a start date prior to or on the first dosing date of study drug and continued to be taken after the first dosing date, or started after the first dosing date but prior to or on the last dosing date of study drug will be considered concomitant medications. Medications started and stopped on the same day as the first dosing date or the last dosing date of study drug will also be considered concomitant. Medications with a stop date prior to the date of first dosing date of study drug or a start date after the last dosing date of study drug will be excluded from the concomitant medication summary. If a partial stop date is entered, any medication with the month and year (if day is missing) or year (if day and month are missing) prior to the date of first study drug administration will be excluded from the concomitant medication summary. If a partial start date is entered, any medication with the month and year (if day is missing) or year (if day and month are missing) after the study drug stop date will be excluded from the concomitant medication summary. Medications with completely missing start and stop dates will be included in the concomitant medication summary, unless otherwise specified. Day 1 to Day 29 medications will follow the same logic of concomitant medications using Day 29 instead of last dosing date of study drug. Summaries will be based on the Safety Analysis Set. No formal statistical testing is planned.

All reported medications will be provided in a by-participant listing sorted by participant ID number and administration date in chronological order.

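### A missing last dose date is imputed as the end of a full course, even for participants recorded as stopping study drug early

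*SAP*

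**What the plan says.** SAP 3.8.1 takes the last dose date from the dosing form, for participants who stopped early as well as for completers, and sends missing dates to Section 4.2. SAP 4.2.1 then applies a rule with an explicit trigger: "If the last study drug dosing date is missing for a participant". The rule picks one date out of a short list and never averages or models; in its words, "the last dose date is imputed as the earliest date from the following". The candidates are:

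- a full-course date set by intake on the first day: "Day 5 if the participant took 2 tablets on Day 1", or one day later (Day 6) for someone with a single tablet that day;
- the date of the final visit in the study.

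The imputed day is capped at Day 6. Duration of exposure is last minus first dosing date plus 1.

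Three other passages bear on the result.

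- SAP 4.2.2 has a separate exposure measure: "The presumed total number of tablets administered to a participant will be determined by the data collected on the drug accountability CRF", computed as dispensed minus returned, with a maximum of 10.
- Protocol 3.3.1.1 keeps early stoppers in follow-up: "If a participant discontinues study drug, every attempt should be made to keep the participant in the study".
- SAP 7.4.2 uses the last dosing date as a cut-off. A medication that "started after the first dosing date but prior to or on the last dosing date of study drug will be considered concomitant medications".

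**The concern.** Neither the record that a participant prematurely discontinued study drug nor the tablet count is a candidate date. The only candidate that can shorten the imputed course is an early last visit. The rule therefore recognises people who left the study but not people who stopped the drug and stayed, and the protocol asks for the latter.

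Early stopping is foreseeable. Protocol 3.3.1.1 stops study drug for certain baseline liver or renal values. Screening laboratory tests are generally optional (Table 1, note i, with country exceptions), and later samples go to a central laboratory (Protocol 6.3.2.5). A disqualifying baseline value can thus come to light after dosing has begun.

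At stake are descriptive safety outputs: the duration table, its agreement with the tablet and disposition tables, and the split between medications taken with study drug and those started afterwards.

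**Working it through.** **Inputs.** Maximum 10 tablets (SAP 4.2.2); one tablet twice daily for 5 days (Protocol 5.3); candidates, cap and duration formula (SAP 4.2.1); Study Day 1 is the first dose date (SAP 3.8.1).

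**1. What Day 5 and Day 6 represent.** With T tablets taken in all, d of them on Day 1 and 2 per day afterwards, the last dosing day is 1 + ceil((T − d)/2).

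- T = 10, d = 2: 1 + ceil(8/2) = Day 5.
- T = 10, d = 1: 1 + ceil(9/2) = Day 6.

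Both SAP figures are reproduced, and both are full-course end dates.

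**2. Overstatement when the date is missing and the last visit is on Day 6 or later.** Duration equals the last dosing day, because L − 1 + 1 = L.

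| Tablets on Day 1 | Imputed duration | True duration | Overstated by |
|---|---|---|---|
| 2 | 5 days | 1, 2, 3, 4 | 4, 3, 2, 1 |
| 1 | 6 days | 1, 2, 3, 4, 5 | 5, 4, 3, 2, 1 |

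The range is 1 to 5 days. If the last visit is on Day 3, the imputed day is 3 and the excess falls to 0 to 2 days for true stops on Days 3 to 1. If the last dose date is recorded, the excess is 0.

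**3. Conflict with the tablet count.** Take 2 tablets on each of Days 1 and 2, then a stop. Accountability gives 4 tablets, while the imputed duration is 5 days, which corresponds to 10 tablets.

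**4. Concomitant medication.** For the same participant, a medication starts on Day 4. Against the true last dose (Day 2), 4 > 2, so it is not concomitant. Against the imputed date (Day 5), 4 ≤ 5, so it is. If it is a COVID-19 antiviral, the table shows a combination that Protocol 5.4.1 prohibits and that did not occur.

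**5. The 30-day window.** A true last dose on Days 1 to 5 closes the window on Days 31 to 35; the imputed date closes it on Day 35 or 36.

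- Laboratory: the last analysis window ends on Day 22 (SAP Table 3-3), inside every version of the 30-day window.
- Adverse events and deaths: the final visit is at latest Day 29 + 5 = Day 34. Up to that visit, only these event days could be reclassified: Days 32–34 (true last dose Day 1), Days 33–34 (Day 2) or Day 34 (Day 3). For a last dose on Day 4 or 5 there are none.

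**6. Efficacy.** Viral-load exclusions and the rescue-medication rule depend on receipt of those treatments (SAP 3.7, 6.4). Censoring uses the Last Study Date, which includes drug end dates and visit dates (SAP 3.8.1). An imputed date cannot be later than the last visit, so it cannot move the censoring date.

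**7. Effect on an arm mean.** The documents give no share affected, so this step is an assumption. Let 1–5% stop early, evenly over Days 1–4, with 2 tablets on Day 1. The mean excess is (4 + 3 + 2 + 1)/4 = 2.5 days.

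- 10% of those dates missing: 0.01 × 0.1 × 2.5 = 0.0025 to 0.05 × 0.1 × 2.5 = 0.0125 day.
- All missing: 0.01 × 2.5 = 0.025 to 0.05 × 2.5 = 0.125 day.

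**The case against.** The strongest reply is that the affected group may be nearly empty. The rule works only on missing dates, and SAP 3.8.1 uses the recorded date for early discontinuers. Protocol 9.1.6 requires start and end dates of study drug in the source records, Protocol 9.1.7 provides for queries, and SAP 2.2 places the final analysis after query resolution. This stands, and it keeps the point small.

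A second reply is that the early stop remains visible. Discontinuations and reasons are tabulated and listed (SAP 4.1), tablets are counted independently, dosing and accountability are listed by participant, and medications from Day 1 to Day 29 are summarised separately from concomitant ones, with rescue medications listed (SAP 7.4.2). This also stands, but it does not correct the duration or the concomitant cut-off; it only lets a careful reader notice the conflict.

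Two stronger readings are tempting. One might infer that every early stopper who stays in the study is analysed as having taken a full course. The text does not support that: a recorded date is used as it is, and even a missing date affects duration only, since tablets come from accountability. One might also infer that the safety tables are materially distorted because their window follows the last dose. On the visit schedule, scheduled laboratory data cannot change classification, and only a few very late events could.

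**Conclusion.** The point holds in a conditional form. When the last dose date is missing, a participant recorded as prematurely discontinuing study drug, but followed past Day 5 or 6, is assigned a full-course duration. The overstatement is 1 to 5 days per affected participant. It can disagree with that participant's tablet count and can misclassify a medication started between the true and the imputed last dose.

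The effect on the 30-day safety window is negligible and no efficacy endpoint is involved. The same rule applies in both arms. The number affected is not stated and is probably small; under the assumptions in the check, an arm's mean duration rises by at most 0.125 day, and by 0.0125 day or less if one in ten of those dates is missing. This is a minor correction to a descriptive analysis.

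**What to change.** In SAP 4.2.1, keep the Day 5/Day 6 rule for participants recorded as completing study drug. For those recorded as prematurely discontinued, add two candidates to the list from which the earliest date is taken:

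- the recorded drug discontinuation date, if the case report form collects one (the documents do not identify such a field);
- the date implied by tablets taken: T = dispensed minus returned, last day = 1 + ceil((T − d)/2), where d is the number taken on Day 1, so that a 1-tablet first day is allowed for.

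Do not use the onset date of the reason for stopping. An adverse event can begin before the last dose: onset on Day 1 with dosing to Day 4 would understate exposure by 4 − 1 = 3 days.

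The cost is one sentence and minor programming. SAP version 1.0 is final, so the change would be documented in the clinical study report, as SAP Section 1 provides. The downside is that the tablet-implied date is slightly early if doses were skipped, and is unavailable if the returned count is missing. An imputed returned count should not stand in for it; if there is no discontinuation date either, the present rule applies.
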